6.5 Efficacy

6.5.1 Study Day and Visit Window Definitions

Study day is defined as the date of assessment – first date of treatment exposure + 1 for assessments that occur on or after the first date of treatment exposure; study day is defined as the date of assessment – first date of treatment exposure for assessments that occur prior to the first date of treatment exposure.

Tumor evaluations prior to first dose are assigned as baseline. Post dosing evaluations/responses during the treatment period will sequentially assigned based on chronology as Tumor Assessment 1, Tumor Assessment 2, etc. including any end of treatment assessments. Assessments collected during follow-up will be similarly assigned based on chronology as Follow-Up Assessment 1, Follow-Up Assessment 2, etc.

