6.5.2 Tumor and Response Evaluations

Tumor and response evaluations, PFS and DOR analyses will be based on the FAS and repeated on the Tumor Response Evaluable Set.

Tumor and response evaluations, PFS and duration of response analyses will be based on the FAS and Tumor Response Evaluable Subjects population. Data will be summarized by dose level in Dose Escalation and by cohort in Dose Expansion, and listed in by-subject listings in the Tumor Response Evaluable Subjects population.

Clinical Benefit Rate (CBR) is the primary endpoint for the Monotherapy Phase 2 and Combination Phase 2 and a secondary endpoint for the Monotherapy Escalation Phase 1, Monotherapy Expansion Phase 1, and Combination Escalation Phase 1. It is defined as the proportion of subjects who have at least one confirmed response of CR or PR (only if subject has measurable disease), or SD \geq 24 weeks (or non-CR/non-PD \geq 24 weeks for subjects with non-measurable disease) prior to any evidence of progression. Subjects who develop PD, intolerable toxicity or death or who discontinue study treatment prior to the first post-Baseline assessment will be classified as non-responders.

A confirmed response of CR/PR means that a response of CR/PR is recorded at one visit and confirmed by repeat imaging at least 4 weeks later with no evidence of progression between confirmation visits.

In case of SD, measurements should have met the SD criteria for a minimum interval of 8 weeks (8 weeks minus the 7-day visit window) following the start of treatment. Similarly, for non-measurable disease, non-CR/non-PD should be maintained for a minimum interval of 8 weeks (8 weeks minus the 7-day visit window) following the start of treatment.

Best overall response (BOR) will be derived for each subject, based on evaluation of response at each tumor assessment visit per investigator assessment using Response Evaluation Criteria in Solid Tumors (RECIST) version 1.1 and reported in the following categories:

- Complete Response (CR)
- Partial Response (PR)
- Stable Disease (SD)
 - SD \geq 24 weeks in duration
 - 8 weeks < SD < 24 weeks in duration
- Non-CR/non-PD
- Progressive Disease (PD)

- Non-Responders (NR)
- Not Evaluable (NE)

Confirmation of PR and CR responses will follow the confirmation process contained in the following table where the best two consecutive time points are considered.

Earlier Best Response (not yet confirmed)	Later Best Response (confirmation)	Best Overall Response
CR	CR	CR

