CR	No CR or missing	SD
PR	CR or PR	PR
PR	SD or PD or missing	SD
SD	NA – no confirmation needed	SD
PD	NA	PD

Responses recorded after initiation of anti-tumor therapy are not used (not evaluable) nor are PD responses after a missed visit [>126 days has elapsed since the last image-based response assessment (or first dose date if no prior response)] up to 24 weeks after C1D1. If the previous evaluable image-based response assessment is more than 24 weeks after C1D1, a PD response is considered to be "missed" if more than 26 weeks (182 days) has elapsed. In the case of stable disease, measurements should have met the stable disease criteria for a minimum interval of 8 weeks (8 weeks minus the 7-day visit window = 49 days) following the start of treatment.

Duration of SD for subjects with best overall response = SD is defined as the time from the day of first study treatment to the start of radiologic disease progression or death. If the subject does not have a radiological disease progression or death, the duration of SD is defined as the time from the day of first study treatment to the date of the last SD assessment. Taking scheduling of imaging into account, a 1 week window will be utilized such that the threshold for 24 weeks will be $23*7 = 161$ [response date – first dose date +1 ≥ 161].

When the investigator is in doubt as to whether progression of disease has occurred and therefore reassesses the subject at a later date, the date of the initial scan should be declared as the date of progression if the repeat scans confirm progression.

Objective Response Rate (ORR) is a secondary endpoint for all cohorts. It is defined as the percentage of subjects with measurable disease who have at least one confirmed response of CR or PR prior to any evidence of progression (as defined by RECIST v1.1). Subjects who develop PD, intolerable toxicity or death or who discontinue study treatment prior to the first post-Baseline assessment will be classified as non-responders.

Data obtained up until progression, or last evaluable assessment in the absence of progression, will be included in the assessment of ORR. However, any complete response or partial response which occurred after a further anticancer therapy was received will not be included in numerator of the ORR calculation.

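### The 7-day allowance for 24 weeks of stable disease is tied to an undefined response date, so progression or death on study days 161–167 can count as clinical benefit

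*SAP*

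**What the plan says.** - **Endpoint.** Protocol 9.4.5.2 counts confirmed CR, confirmed PR in measurable disease, and SD that has lasted 24 weeks or more before progression appears. SAP 6.5.2 adds non-CR/non-PD of at least 24 weeks "for subjects with non-measurable disease) prior to any evidence of progression". CBR is primary in Monotherapy Phase 2 and Combination Phase 2, and secondary in the Phase 1 parts.
- **SD duration (SAP 6.5.2).** When best overall response is SD, duration is "the time from the day of first study treatment to the start of radiologic disease progression or death". With neither event, "the duration of SD is defined as the time from the day of first study treatment to the date of the last SD assessment".
- **24-week test.** The threshold is lowered by one week to 161 days and written as "response date – first dose date +1 ≥ 161". Neither document defines the response date.
- **Day count (SAP 6.5.1).** Study day is "the date of assessment – first date of treatment exposure + 1 for assessments that occur on or after the first date".
- **Missed scans (SAP 6.5.2).** Not used in the response derivation are responses after new anti-tumor therapy, "nor are PD responses after a missed visit [>126 days has elapsed since the last image-based response assessment". Death is not mentioned.
- **Scans (Protocol 1.3, footnote 16).** Weeks 8, 16 and 24, each ± 7 days.
- **Non-CR/non-PD.** No end date is given for its duration. The best-response list divides SD at 24 weeks (one category is "8 weeks < SD < 24 weeks in duration") but does not divide non-CR/non-PD.

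**The concern.** A visit-window allowance normally serves a patient whose scan comes a few days early and still shows no progression. Here the duration to which it applies ends at PD or death. It therefore shortens the required progression-free time itself, and a subject known to have progressed before 24 weeks can be scored as a clinical benefit.

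The undefined term adds a second problem. If the response date is the end of the SD duration, PD first seen at week 24 completes the 24 weeks. If it is the date of an SD assessment, the same subject fails. The primary endpoint could then take two values from one dataset.

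**Working it through.** **1. The plan's threshold.** 24 × 7 = 168 days; 168 − 7 = 161 = 23 × 7. This reproduces the SAP figure.

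**2. Study days of in-window scans** (elapsed days + 1):

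| Scan | Nominal day | Window |
|---|---|---|
| Week 8 | 57 | 50–64 |
| Week 16 | 113 | 106–120 |
| Week 24 | 169 | 162–176 |

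**3. SD at weeks 8 and 16, PD first seen at week 24.**
- Duration to PD: 162–176, always at least 161, so the subject counts.
- Response date = last SD scan: 106–120, always below 161, so the subject does not count.

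**4. Does the missed-visit rule remove that PD?** The gap from week 16 to week 24 is 42–70 days. From week 8 to week 24 it is 162 − 64 = 98 to 176 − 50 = 126 days. Exclusion needs more than 126, so it never applies, even when week 8 was the only SD scan.

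**5. Direct conflict with Protocol 9.4.5.2.** PD or death on study days 161–167 passes the test but falls short of 168 days. From day 168 the 24 weeks are literally met. Of the 15 in-window week-24 days, 162–167 are short: 6/15 = 40%.

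**6. Side effects of the duration rule.**
- A subject with SD at week 16 and no later scan, PD or death is judged at about Day 113 and fails. An otherwise identical subject with PD at week 24 passes.
- One SD scan on Day 57 and death on Day 200 gives a duration of 200 days and passes. The gap is 200 − 57 = 143 days, so SAP Table 3, row 3, censors that subject's PFS at week 8.
- In the other direction, a first PR at week 24 with no later scan becomes SD, because the confirmation table maps PR followed by "SD or PD or missing" to SD. Its last assessment recorded as SD is week 16, so read literally it fails.

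**7. Illustrative size.** Let h be the share of subjects without PD at week 16 who have best response SD and show PD at week 24, with all scans done. Then CBR(duration rule) = CBR(non-PD-scan rule) / (1 − h). The documents do not give h. Assume exponential PFS with the medians in Protocol 2.1, so that h = 1 − 2^(−56/median in days):

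| Median (months) | Days | h | 40% reads as | Extra points | Extra per 75 |
|---|---|---|---|---|---|
| 4.6 (fulvestrant alone) | 140.0 | 24.2% | 52.8% | 12.8 | 9.6 |
| 9.5 (palbociclib + fulvestrant) | 289.2 | 12.6% | 45.7% | 5.7 | 4.3 |

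Under these assumptions each h is an upper bound. Confirmed responders who progress by week 24 count under either rule, and deaths before Day 161 count under neither.

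Direct-conflict part at the 4.6-month median: if scans spread evenly over the window, 0.40 × 12.8 = 5.1 points (3.8 per 75); if every scan falls on Day 169, zero. It would be larger only if scans ran systematically early.

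**8. Scale.** For 30/75 the exact 95% interval is 28.9% to 52.0%, a half-width of 11.6 points, which agrees with the planned ± 12%.

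**The case against.** The strongest reply is that SAP 6.5.2 contains one rule with a loose label. The paragraph defines duration and then applies a threshold to it. The best-response category is itself worded in terms of duration, and the SAP elsewhere treats PD as a response, so a response date can include a PD date. Tying the test to SD scans would also leave the PD or death end date with no role in it. This is the more natural reading, and it stands. It does not rescue days 161–167, because on that reading the allowance falls on the event date.

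Second, no passage requires a non-PD scan near week 24. PD from day 168 onward satisfies the protocol literally, so a reader who infers that every week-24 progression credited as benefit breaches the protocol goes too far. For those subjects the issue is ambiguity, not contradiction.

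Third, several consequences are edge cases. PFS censoring need not govern CBR, failing a subject last scanned at week 16 is conservative handling of missing data, and the undivided non-CR/non-PD category is only a display omission. These points are fair. The missing end date for non-CR/non-PD is a real gap, since CBR depends on it.

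Fourth, all analyses are descriptive, and the SAP treats Combination Phase 2 as conditional (5.2 and 7). This limits the consequences but leaves Monotherapy Phase 2 affected.

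**Conclusion.** The point holds. As written, the SAP credits PD or death on study days 161–167 as SD of at least 24 weeks, in direct conflict with Protocol 9.4.5.2. For PD at in-window week-24 scans from day 168, the result depends on an undefined term. It affects Monotherapy Phase 2, CBR as a Phase 1 secondary endpoint, and Combination Phase 2 if that part is executed.

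The size is illustrative only. It rests on an exponential curve, borrowed medians and complete scanning: at most about 13 points at a 40% CBR with the 4.6-month median, of which 0 to about 5 points are direct conflict with on-schedule to evenly spread scans. Progression in this trial's own population may differ.

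Two stronger inferences are tempting. One is that CBR is biased against the 40% and 56% benchmarks in Protocol 9.2.3; the documents do not say how those studies counted such subjects, so no direction is shown. The other is that the rule was chosen with results in view, because the SAP (17 February 2023) follows the 18 May 2022 data cut-off. SAP Section 4 places SAP finalization before database lock and analysis, and nothing in the documents shows such a choice.

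**What to change.** In SAP 6.5.2, for the CBR derivation:
- Define the response date as the date of an evaluable non-PD assessment (SD or better, or non-CR/non-PD).
- Count SD or non-CR/non-PD of at least 24 weeks only if such an assessment falls on or after Day 161, with no PD, death or new anti-cancer therapy on or before it.
- Keep time to PD or death as the descriptive SD duration.
- Report CBR under the current duration rule as a sensitivity analysis. This also covers subjects who miss the week-24 scan and progress later.
- Record the 161-day allowance in SAP Section 8. It parallels the 7-day allowance that Protocol 9.4.5.1 uses for the 8-week SD minimum, so it needs noting, not removing.

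**Cost.** Wording and one derivation; no new data. CBR may be slightly less favourable. A subject who misses the week-24 scan and then has PD no longer counts in the primary derivation, even if that PD comes well after 24 weeks. A small residue of the allowance remains: a non-PD scan on Day 162 followed by PD on Day 166 would still count, which is a further reason to state the allowance openly. The change itself comes after the data cut-off, so the reason for it should be documented and both results shown.

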- 16. Tumor evaluation by CT/MRI or applicable scan will be performed during Screening (within 28 days of Cycle 1 Day 1) and every 8 weeks (± 7 days) after C1D1 for the first 24 weeks. After 24 weeks, scans may be performed every 12 weeks (± 7 days). The same radiographic procedure used to define measurable lesions must be used throughout the study for each subject. Applicable scans to be done at EOT visit if not done within the previous 4 weeks.
- 17. Plasma samples for 4β -hydroxycholesterol and cholesterol will be collected pre-dose on C1D1, C1D15, and pre-dose on Day 1 of Cycles 2-4 of the Monotherapy Dose Escalation and Expansion.
- 18. A FES-PET scan (optional) should be conducted at Screening and at least after 1 month of treatment (preferably within the first 2 months, in Cycle 2).
- 19. Beginning on C1D1, subjects will take ZN-c5 once daily (alternatively, this total daily dose may be divided by 2 and administered BID [every 12 hours]). ZN-c5 dosing and administration as per assigned cohort (see Section 6.1.2.1).
- 20. In Phase 1, beginning on C1D1, subjects in the combination treatment cohorts will take palbociclib at the label indicated dose of 125 mg orally once daily (2 hours after the ZN-c5 dose was taken) for 21 consecutive days followed by 7 days off treatment (1 cycle of treatment = 28 days) (see Section 6.1.2.2). In Phase 2, subjects in the combination treatment cohorts will take palbociclib at the label indicated dose of 125 mg orally once daily (at the same time the ZN-c5 dose is taken) for

- 21 consecutive days followed by 7 days off treatment (1 cycle of treatment = 28 days).21. Disease Assessment Follow-up Visit: Subjects without progression of disease (PD) at the time of study drug discontinuation will continue to undergo disease evaluations every 12 weeks \pm 7 days until confirmation of PD, initiation of the first subsequent cancer therapy, withdrawal of consent, death, loss to follow-up, or until the study is terminated. Once a subject has confirmation of PD or has initiated subsequent cancer therapy, whichever occurs first, disease follow-up will discontinue.
- 22. Long-term Follow-up (LTFU) Subjects will be contacted every 3 months (phone or medical records) for survival status and collection of subsequent breast cancer treatments.

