9.4.7 PLANNED INTERIM ANALYSES

An interim futility analysis will be conducted after Stage 1 accrual for each dose cohort in the Combination Phase 2 and necessary minimum follow-up is complete. The guiding futility criteria are presented in Section 9.2, Sample Size Determination.

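### SAP 6.5.2 ends SD duration at the last scan labelled SD, so a progression-free subject whose first response is at week 24 fails CBR if no usable scan follows

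*SAP*

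**What the plan says.** SAP 6.5.2 states that "Clinical Benefit Rate (CBR) is the primary endpoint for the Monotherapy Phase 2 and Combination Phase 2". A subject succeeds with a confirmed CR or PR (PR only with measurable disease), or with SD of at least 24 weeks. For non-measurable disease, non-CR/non-PD of at least 24 weeks takes the place of SD. Confirmation needs repeat imaging at least 4 weeks later.

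The confirmation table in the same section gives a best overall response of SD to a PR followed by "SD or PD or missing", and likewise to a CR not followed by CR. Such subjects then come under the SD-duration rule, which has two branches:

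- With an event, the duration "is defined as the time from the day of first study treatment to the start of radiologic disease progression or death".
- Without one, "the duration of SD is defined as the time from the day of first study treatment to the date of the last SD assessment".

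The threshold is 161 days, which is 24 weeks less a one-week window.

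Protocol 1.3 (footnote 16) and 8.1.1 place scans every 8 weeks (± 7 days) for 24 weeks. Then "After 24 weeks, scans may be performed every 12 weeks". Protocol 9.4.7 puts the Combination Phase 2 futility look after Stage 1 accrual, once "necessary minimum follow-up is complete". The length of that follow-up is not given.

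**The concern.** The confirmation table changes the subject's best overall response. Nothing in the SAP relabels the individual visit. A week-24 scan read as PR or CR is therefore not, on the text, an SD assessment, and the event-free branch goes back to week 16. A subject whose tumour shrinks at week 24 can then score worse than one whose tumour is unchanged.

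This matters because CBR is primary in both Phase 2 parts and drives the Stage 1 rule of at least 11 of 19. The misclassification can only lower CBR. The confirming scan can be absent for ordinary reasons: an interim look taken before week 36, the 18 May 2022 data cut-off (the limited data that SAP section 8 lists for later collection include no tumour scans), new anticancer therapy (later responses are not used), or loss to follow-up.

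There is a related gap. Subjects with non-measurable disease have scans labelled non-CR/non-PD, never SD, so the event-free branch gives them no end date.

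**Working it through.** **Inputs.** Scans at weeks 8, 16 and 24, then week 36 (Protocol 1.3, 8.1.1). Threshold: response date − first dose date + 1 ≥ 161 (SAP 6.5.2). Simon design: CBR 50% against 70%, one-sided 0.025, 80% power, 19 + 32 = 51 evaluable, continue with at least 11 of 19, early-stopping probability 68% (Protocol 9.2.4, SAP 3.5.4).

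**The plan's own figures.** Threshold: 23 × 7 = 161 days, as stated. Early stopping: P(X ≤ 10 | 19, 0.50) = 0.676, against the stated 68%.

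**Rule applied to scan sequences.** Study day on schedule = 7 × week + 1, so weeks 8, 16, 24 and 36 are days 57, 113, 169 and 253. Every row starts with SD at days 57 and 113.

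| Week 24 | Afterwards | Duration on the literal text | CBR |
|---|---|---|---|
| SD | no later scan needed | 169 | benefit |
| PR | no usable scan | 113 | failure |
| CR | no usable scan | 113 | failure |
| CR | PR at week 36 only | 113 | failure |
| PR | PR at week 36 | confirmed response | benefit |
| PR | SD at week 36 | 253 | benefit |
| PR | PD at week 36 | 253 (event branch) | benefit |

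Visit windows do not rescue the failing rows. The latest in-window week-16 scan is day 113 + 7 = 120, still below 161. The earliest in-window week-24 scan is day 169 − 7 = 162, so counting the week-24 visit would always meet the threshold. An unscheduled SD scan on or after day 161 would also rescue the subject.

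**Cost per subject.** 1/75 = 1.3 percentage points at the planned Monotherapy Phase 2 size per dose level. 1/19 = 5.3 points in Stage 1.

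**Illustration at the final Combination Phase 2 analysis.** The final cut-off is not stated. Rejecting at 33 or more of 51, after passing Stage 1, gives exact one-sided alpha 0.0219 and power 0.801, which fits the stated 0.025 and 80%. One more success allowed (32 or more) gives alpha 0.039, above the limit.

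Let m be the share of all subjects actually misclassified, so that a true CBR of 0.70 is measured as 0.70 − m. Suppose 5% have a first response at week 24 and 10–20% of those have no later usable scan (both assumed). Then m = 0.05 × 0.10 = 0.5% to 0.05 × 0.20 = 1%.

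| m (assumed) | Measured CBR | Power, ≥ 33/51 |
|---|---|---|
| 0 | 70.0% | 80.1% |
| 0.5% | 69.5% | 78.0% |
| 1% | 69.0% | 75.7% |

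**Stage 1 look.** The share can be larger here because recent enrollees may not have reached week 36. P(at least 11 of 19) is 91.6% with none misclassified. It is 88.1% if 2% of the Stage 1 subjects are misclassified at the look, and 81.5% if 5% are (both shares assumed).

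**The case against.** The best defence is that a benign reading is available. The threshold formula refers to a response date, not an SD date. Protocol Table 12 classes PR or CR followed by a non-evaluable scan as SD if the minimum SD duration is met, which suggests that a downgraded response visit may itself serve as an SD assessment. Both are hints. The SAP states neither as a rule, and a programmer following its sentence would code a failure. Two programmers could derive different primary-endpoint values from one text.

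The CR-then-PR row is also narrow. The footnote to Table 12 says disease seen after a true CR is PD, or that the CR should be re-read as PR. The failure arises only where the recorded labels stay CR and then PR.

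A reader might infer more: that every subject with a first response at week 24 is lost, so that if 2% or 5% of subjects respond first at week 24, power drops to 70.9% or 54.4%. The documents do not support that. A week-36 PR, SD or PD after a week-24 PR restores benefit. Subjects who stop treatment without PD continue with scans every 12 weeks (Protocol 7.6), and an end-of-treatment scan is due if none was done in the previous 4 weeks.

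Nor do the documents support calling the error systematic at the futility look. The look is not fixed at 24 weeks, earlier enrollees may already have week-36 scans, and additional scans are allowed when clinically indicated.

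It also stands that the Stage 1 consequence applies only if that part is run (SAP 5.2 says so), that no formal hypothesis test is planned, and that the bias is conservative. For non-measurable disease, SAP 6.5.2 does define success as non-CR/non-PD for at least 24 weeks. Only the end date is missing.

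**Conclusion.** The sentence is wrong as written and needs correcting, within a limited scope. It misclassifies progression-free subjects whose first response is at week 24 and is their last usable scan, plus those recorded as CR at week 24 and then only PR. It also leaves the event-free end date undefined for non-CR/non-PD subjects.

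The result does not follow from the protocol, whose CBR definition (9.4.5.2) asks only that SD last 24 weeks before any evidence of progression. It also departs from the SAP's PFS rules, which accept CR, PR and SD scans alike as evaluable. SAP section 8 does not list it as a change from the protocol.

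The number affected cannot be found from the documents. The firm figures are 1.3 points of CBR per subject at n=75 and 5.3 points at n=19, always downward. The fall in power from about 80% to 78–76% is an illustration. It rests on an assumed 0.5–1% misclassified at the final analysis and on the inferred cut-off of 33 of 51. The effect at an early Stage 1 look may be larger, but only through subjects without a week-36 scan.

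**What to change.** In SAP 6.5.2, replace the end date in the event-free branch with: *the date of the last evaluable assessment without PD (SD, non-CR/non-PD, PR or CR, confirmed or not) before any new anticancer therapy*. Apply the 161-day test to that date. Name the four labels explicitly, because the evaluable-assessment definition under the SAP's PFS censoring table omits non-CR/non-PD.

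With this wording, SD, SD, then an unconfirmed PR or CR at week 24 has a duration of 169 days (162 at the earliest in-window scan) and counts as clinical benefit, as SD at week 24 already does.

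The cost is one sentence in the SAP and one line in the derivation program. No new data are needed.
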